8.6.3 Criteria for Treatment Interruption and Dose Reduction

All toxicities that occur during the study will be actively managed following the standard of care unless otherwise specified in the protocol.

8.6.3.1 Modakafusp Alfa Dose Modification Guidelines

[Table 8.b](#) provides general dose modification recommendations for modakafusp alfa. When the dose of modakafusp alfa is withheld on the basis of these criteria, clinical and laboratory re-evaluation should be repeated at least weekly or more frequently, depending on the nature of the toxicity observed, until the toxicity resolves to Grade ≤ 1 or baseline. If there are transient laboratory abnormalities that, based on investigator assessment, are not clinically significant, continuation of therapy without dose modification is permissible upon discussion with the sponsor. See details for managing specific AEs in [Section 8.10](#).

Table 8.b Dose Modification Recommendations for Toxicities Possibly Related to Modakafusp Alfa

Criteria	Action
Grade 1 AEs	No dose reductions or interruptions.
Grade 2 AEs	Patients experiencing Grade 2 AEs considered related to study treatment that are not easily managed or corrected and are not tolerable to the patient, or AEs that are not acceptable in the investigator's judgment, should have study treatment interrupted until the AE resolves to Grade ≤ 1 or baseline and then restarted at the same dose or, depending on the toxicity, at the previous safe dose level or below.
Grade 3, Grade 4 (not life-threatening per seriousness criteria), and Grade 4 asymptomatic laboratory AEs	Hold modakafusp alfa until resolution to Grade ≤ 1 or baseline, and then resume treatment at a reduced dose level. In case of Grade 3 hematological toxicity (anemia, thrombocytopenia, neutropenia, or lymphopenia) or Grade 3 asymptomatic laboratory AEs, the patient can continue at the same dose or a reduced dose at the investigator's discretion.
Grade 4 (life-threatening per seriousness criteria) AEs	Permanently withdraw the patient from the study.
AEs of all grades	If treatment has been held for >14 consecutive days without resolution of the toxicity (to baseline or Grade ≤ 1), consider permanently discontinuing study treatment unless there is clinical benefit for the patient as assessed by the investigator and with sponsor's approval. Treatment can be resumed at a reduced dose level after resolution of AEs to Grade ≤ 1 or baseline.

AE: adverse event.

When a dose reduction occurs, the modakafusp alfa dose will be reduced to the next lower dose that has been established as a safe dose during dose escalation. If initial dose adjustment does not provide sufficient relief, the dose of modakafusp alfa can be further reduced if the treating physician considers that the patient is receiving benefit. In general, after a dose is reduced, it should not be re-escalated even if there is minimal or no toxicity with the reduced dose. However, if further evaluation reveals that the AE that led to the dose reduction was not study drug related, the dose may be re-escalated to the original dose level. If more than 2 dose reductions are required for the same AE, the patient should be discontinued from therapy.

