6.3 Duration of Study

6.3.1 Duration of an Individual Patient's Study Participation

Patients may receive modakafusp alfa as a SA for up to 1 year or in combination with pembrolizumab for up to 2 years. Patients with demonstrated clinical benefit can continue treatment beyond those points if approved by the sponsor. These patients can continue receiving treatment in this study or in any of the poststudy access modalities described in the protocol (Section 6.3.5). Patients may discontinue treatment when they meet any of the discontinuation criteria stated in the protocol (Section 9.6).

All patients will have an EOT visit 30 days (+10 days) after receiving the last dose of study drug or before the start of subsequent systemic anticancer therapy, whichever occurs first, to permit detection of any delayed TEAEs and to resolve any ongoing events. Patients with unresolved TEAEs will continue the periodic safety follow-up until complete resolution or stabilization (established as sequelae) occurs.

Patients who discontinue study treatment for reasons other than progressive disease (PD) will continue PFS follow-up every 12 ± 1 weeks from the EOT visit until the occurrence of PD, lost to follow-up, consent withdrawal, death, start of subsequent systemic anticancer therapy, or study termination, whichever occurs first. After disease progression or starting another systemic anticancer therapy, all patients will be followed every 12 ± 1 weeks for OS until death or study termination.

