8.6.4.1 Criteria for Discontinuing Modakafusp Alfa

Study drug **must** be permanently discontinued if any of the following criteria are met:

1. Patient experiences an AE in Cycle 1 meeting criteria for a DLT that is considered life-threatening.
2. Confirmed progressive disease according to RECIST v1.1.
3. Start of new/subsequent anticancer treatment.
4. Confirmed pregnancy.
5. Patient meets any of the criteria for discontinuation specified in Section 8.10.

Study drug **may** be discontinued after discussion with the study sponsor, if any of the following criteria are met:

1. Any non-life-threatening AEs if the investigator determines that study continuation is no longer in the patient's best interest.
2. Any AE that changes the benefit-risk assessment for a patient.

3. Clinical deterioration of the patient as assessed by the investigator.
4. CR.
5. Unsatisfactory therapeutic response.
6. Study terminated by sponsor.
7. Withdrawal by subject.
8. Subject's death.
9. Lost to follow-up.
10. Delay of next cycle by more than 14 days.
11. Important protocol deviations from inclusion/exclusion criteria.

If treatment is discontinued, the EOT visit should be completed within 30 to 40 days after the last administration of modakafusp alfa.

8.6.4.2 *Criteria for Discontinuing Pembrolizumab*

Pembrolizumab will be discontinued if any of the criteria described in [Table 8.c](#) or the pembrolizumab SmPC have been met. Additionally, pembrolizumab may be discontinued for other reasons if it is considered in the best interest of the patient and discussed with the medical monitor.

Permanently discontinue pembrolizumab for any of the following:

- Any life-threatening adverse reaction (excluding endocrinopathies controlled with hormone replacement therapy).
- Grade 3 or 4 pneumonitis or recurrent pneumonitis of Grade 2 severity.
- Grade 3 or 4 nephritis.
- Grade 4 severe skin reactions or confirmed Stevens-Johnson syndrome or toxic epidermal necrolysis.
- AST or ALT greater than $5 \times \text{ULN}$ or total bilirubin greater than $3 \times \text{ULN}$.
 - For patients with liver metastases who begin treatment with Grade 2 AST or ALT, if AST or ALT increases by greater than or equal to 50% relative to baseline and lasts for at least 1 week.
- Grade 3 or 4 IRRs.
- Inability to reduce corticosteroid dose to 10 mg or less of prednisone or equivalent per day within 12 weeks of an irAE.

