9.4 Completion of Study (for Individual Patients)

Patients will be considered to have completed the study if they are discontinued from study drug and 1 or more of the following situations occur:

- Death.
- Consent withdrawal.
- Investigator decision.
- Study terminated by the sponsor.
- Lost to follow-up.
- Transfer of patient to a long-term safety study or similar program.

The consequence of consent withdrawal is that no new information will be collected from the withdrawn patient and added to the existing data or any database.

Once study has been completed, all study procedures outlined for the end of study visit will be completed as specified in the SOE ([Appendix A](#)). After study completion, no new information will be collected from the completed patient and added to the existing data or any database.

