9.5 Discontinuation of Modakafusp Alfa Treatment and Patient Replacement

Treatment must be permanently discontinued if any of the criteria detailed in Section [8.6.4](#) are met.

Once study drug has been discontinued, all study procedures outlined for the EOT visit will be completed as specified in [Appendix A](#). The primary reason for study drug discontinuation will be recorded on the eCRF.

During Cycle 1 of the dose escalation phase, patients who are discontinued prematurely for reasons other than a DLT will be replaced.

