9.7 Posttreatment Follow-up Assessments (PFS and OS)

Patients who stop treatment for any reason other than PD will continue to have PFS follow-up visits. The PFS follow-up should occur every 12 ± 1 weeks from the EOT until the occurrence of progression, death, the start of subsequent systemic antineoplastic therapy, study termination, or until 6 months after the discontinuation of study treatment, whichever occurs first.

After disease progression or starting another systemic anticancer therapy, all patients will be followed every 12 ± 1 weeks for OS until death or study termination. Survivor information and death details may be collected by methods that include, but are not limited to, telephone, e-mail, mail, or retrieval from online or other databases (eg, Social Security indexes). In addition, the start of another anticancer therapy for the disease under study will be collected.

See [Appendix A](#) for appropriate assessments during follow-up.

NOTE: Treatment-related SAEs must be reported to the Global Pharmacovigilance department or designee. This includes deaths that the investigator considers related to study drug that occur during the posttreatment follow-up. Refer to Section [10.0](#) for details regarding definitions, documentation, and reporting of SAEs.

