- ⁱ Blood samples for TBNK (T cells [including CD4+ and CD8+ T cells], B cells, and NK cells) flow cytometric analysis will be obtained predose on indicated visits, only if local analysis is available at the site.
- ^j Urinalysis (dipstick) will include tests listed in [Table 9.a](#). Microscopic if clinically indicated only: bacteria, RBCs, WBCs, casts, and crystals.

-
- ^k A serum or urine pregnancy test will be performed for patients of childbearing potential with negative results during screening and again at C1D1 (baseline) if the screening test was performed more than 72 hours before the C1D1 dosing. A serum or urine pregnancy test must be performed at predose (within 72 hours prior to dosing) on Day 1 of each cycle with negative results available before modakafusp alfa is administered. A serum or urine pregnancy test is required at EOT.
- ^l At least 1 target lesion amenable for biopsy is required for enrollment in phase 1b. The accessible biopsy lesion should not have been previously irradiated. See Section 9.3.15.2 for details.
- ^m Blood samples for modakafusp alfa PK will be collected at timepoints specified in Table 16.f below.
- ⁿ Immunoprofiling consists of mass cytometric analysis of T, B, and NK lymphocyte subsets, and will be analyzed centrally.
- ^o Predose.
- ^p Predose and at 4 hours (+/- 30 minutes) after the end of infusion.
- ^q Blood samples for immunogenicity (ADA) testing will be collected before the dose on Day 1 of every cycle while the patient remains in treatment and, if possible, at the EOT follow-up visit. In case of an infusion reaction, blood draws should be performed for central evaluation of immunogenicity.
- ^r One blood sample for DNA will be taken at either screening or C1D1 predose (when it is not possible to collect at screening, samples can be collected at the next visit).
- ^s Patients who discontinue modakafusp alfa for reasons other than PD will continue PFS follow-up every 12±1 weeks from the EOT visit until the occurrence of PD, death, the start of subsequent systemic anticancer therapy, study termination, or until 6 months after the discontinuation of study treatment, whichever occurs first. PFS will be assessed according to RECIST v1.1 (Section 9.3.14.1).

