- ^r Blood samples for immunogenicity (ADA) testing will be collected before the dose on Day 1 of every cycle while the patient remains in treatment and, if possible, at the EOT follow-up visit. In case of an IRR, blood draws should be performed for central evaluation of immunogenicity.
- ^s One blood sample for DNA will be taken at either screening or C1D1 predose (when it is not possible to collect at screening, samples can be collected at the next visit).
- ^t Patients who discontinue modakafusp alfa for reasons other than PD will continue PFS follow-up every 12±1 weeks from the EOT visit until the occurrence of PD, death, the start of subsequent systemic anticancer therapy, study termination, or until 6 months after the discontinuation of study treatment, whichever occurs first. PFS will be assessed according to RECIST v1.1.
- ^u Patients will be followed for survival every 12±1 weeks until death, loss to follow-up, consent withdrawal, or study termination. Survivor information and death details may be collected by methods that include, but are not limited to, telephone, e-mail, mail, or retrieval from online or other databases (eg, Social Security indexes). In addition, the start of another anticancer therapy for the disease under study will be collected.
- ^v A sample for blood typing to be taken only at screening. Blood banks need to be alerted that the patient is going to receive an anti-CD38 antibody that may interfere with blood typing in a manner similar to daratumumab. If the blood bank issues a compatibility card, it should be made available to the patient. The patient needs to tell other healthcare providers that he/she is receiving an anti-CD38 antibody if, for example, a blood transfusion is needed.
- ^w A whole blood sample will be collected to quantify CTCs at baseline and correlate with response.

- ^x Pharmacodynamic samples to be collected for patients enrolled within the safety lead-in and those enrolled within the expansion cohorts prior to futility being met.
- ^y After futility has been met within an expansion cohort, the on-treatment biopsy sample should be taken prior to Cycle 3 administration of modakafusp alfa and pembrolizumab. For convenience, biopsy can be taken up to a 7 days prior to C3D1, preferably to coincide with imaging assessments of disease.

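### Table 8.b withdraws patients with a life-threatening Grade 4 AE from the study, whereas 6.3.1, 9.7 and the Schedule of Events footnotes keep PFS and OS follow-up after any non-PD treatment stop

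*Protocol*

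**What the plan says.** Protocol 8.6.3.1, Table 8.b, gives this action for a Grade 4 AE that is life-threatening by the seriousness criteria: "Permanently withdraw the patient from the study". The next row, for AEs of all grades, speaks of discontinuing study treatment.

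The follow-up rules are set elsewhere:

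- Protocol 6.3.1 gives every patient an EOT visit and then states: "Patients who discontinue study treatment for reasons other than progressive disease (PD) will continue PFS follow-up every" 12 ± 1 weeks. It follows all patients for OS after progression or new systemic therapy, until death or study termination.
- Protocol 9.7: "Patients who stop treatment for any reason other than PD will continue to have PFS follow-up visits". It has the same OS rule.
- Schedule of Events footnotes s (phase 1b) and t (phase 2): "Patients who discontinue modakafusp alfa for reasons other than PD will continue PFS follow-up every" 12 ± 1 weeks. Footnotes t (phase 1b) and u (phase 2) continue survival contact every 12 ± 1 "weeks until death, loss to follow-up, consent withdrawal, or study termination".

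Two further sections treat the action as stopping drug. Protocol 8.6.4.1 lists, among the triggers for permanently stopping study drug, "Patient experiences an AE in Cycle 1 meeting criteria for a DLT that is considered life-threatening", and asks for an EOT visit 30 to 40 days after the last dose. Protocol 9.5 says: "Once study drug has been discontinued, all study procedures outlined for the EOT visit will be completed as specified in" Appendix A.

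Protocol 9.4 states what leaving the study means: "After study completion, no new information will be collected from the completed patient and added to the existing data or any database".

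**The concern.** The protocol separates stopping treatment from leaving the study, and SAP 7.4 tabulates the reasons for each separately. A site could therefore take the Table 8.b row as the stronger action. Section 9.4 offers a possible route: a patient off drug completes the study on, among other things, an investigator decision, and data collection then ends.

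Tumor and survival follow-up would then stop because of severe toxicity. Under SAP 7.9, PFS would be censored at the last assessment of SD or better, or on day 1 if there was no post-baseline assessment. OS would be censored at the date last known alive. Censoring triggered by severe toxicity is unlikely to be independent of outcome, and these are single-arm cohorts of up to 25 with no comparator to offset the bias.

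**Working it through.** The plan gives no figure to reproduce. The check compares the texts and then bounds the effect.

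**1. What each section supports**

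| Place | Drug stop only | EOT | PFS follow-up | OS follow-up | Toxicity exception |
|---|---|---|---|---|---|
| Table 8.b, life-threatening Grade 4 row | No: leaves study | not stated | not stated | not stated | n/a |
| 6.3.1 | Yes | Yes | Yes | Yes | None |
| 9.7 | Yes | refers to it | Yes | Yes | None |
| Schedule of Events and footnotes | Yes | Yes | Yes | Yes | None |
| 8.6.4.1 | Yes (life-threatening Cycle 1 DLTs; 8.10 criteria) | Yes | silent | silent | n/a |
| 9.5 | Yes | Yes | silent | silent | None |

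The direct conflict is with 6.3.1, 9.7 and the footnotes. Sections 8.6.4.1 and 9.5 support only drug discontinuation plus EOT.

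**2. Where the protocol already resolves it.** Section 8.6.3.1 refers to 8.10 for specific AEs. Table 8.f withdraws a patient with a life-threatening Grade 4 infusion reaction from treatment. Section 8.10.2 withdraws a patient with a platelet count below 10 × 10⁹/L, or with bleeding attributed to thrombocytopenia, from modakafusp alfa treatment, with an exception for clinical benefit. The conflict remains for other life-threatening Grade 4 AEs.

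**3. Contacts at stake per patient.** Assume 12 to 25 months of study remain after the last dose. EOT is at day 30 to 40; contacts follow every 84 days.

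- 12 months: (12 × 30.4375 − 40)/84 = 3.87 to (12 × 30.4375 − 30)/84 = 3.99, so 3 contacts.
- 25 months: (25 × 30.4375 − 40)/84 = 8.58 to (25 × 30.4375 − 30)/84 = 8.70, so 8 contacts.

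PFS visits: the first falls at day 107 to 131 (30 + 77 to 40 + 91), the second at day 191 to 215 (30 + 161 to 40 + 175). The 6-month cap in 9.7 and the footnotes is day 182.6 if counted from the last dose, so one visit fits. If discontinuation is dated 9 or more days after the last dose, a second can fit. Section 6.3.1 has no cap.

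**4. Upper bound for OS.** Suppose k of 25 patients are censored before any other death and die, unrecorded, before the landmark. With survival S in the others, Kaplan-Meier gives S, the true value is S × (1 − k/25), and the overstatement is S × k/25.

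| k | S = 40% | S = 80% |
|---|---|---|
| 1 | 0.40 × 0.04 = 1.6 points | 0.80 × 0.04 = 3.2 points |
| 2 | 0.40 × 0.08 = 3.2 points | 0.80 × 0.08 = 6.4 points |

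S and k are assumptions. For scale only, Protocol 8.5 requires related, life-threatening, nonhematologic Grade 4 AEs to stay below 10% once 30 patients are dosed; 10% of 25 is 2.5, so at most 2. That is a trial-wide monitoring ceiling, not an expected rate.

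**5. Which deaths would be missed.** Section 10.3 requires all SAEs to be reported for 30 days after the last dose, serious irAEs for 90 days, and related SAEs after that. Section 9.7 extends this to related deaths in post-treatment follow-up, and 10.2 follows each SAE to resolution or permanent outcome. The loss is therefore mainly of later deaths judged unrelated.

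**The case against.** The strongest reply is that this is a slip in a table of dose-modification recommendations, and that follow-up is governed by 6.3.1, 9.7 and the Schedule of Events, which are clear. Comparable severe-toxicity provisions (8.6.2, Table 8.f, 8.10.2) speak of withdrawal from treatment. Section 8.10 also covers two of the more frequent toxicities reported at the January 2021 cutoff: infusion reactions (8 of 17 patients) and thrombocytopenia (5 of 17). Harm needs three steps: a literal reading, coding as study completion, and disregard of 9.7 and the footnotes. The affected endpoints are secondary and carry no formal test.

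Most of this stands, and it limits the size. It does not remove the conflict. The row is current text, and the neighboring row uses *study treatment*, so a reader cannot be sure that the two words mean the same thing.

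Four stronger inferences are tempting but unsupported:

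- That all the cited sections preserve EOT, PFS and OS follow-up. Sections 8.6.4.1 and 9.5 reach only EOT, and for most later-cycle events 8.6.4.1 is silent rather than opposed.
- That any later death would be lost. Related deaths remain reportable.
- That 9.4 closes the record automatically. Its list has no adverse-event entry, and a protocol-directed withdrawal is not plainly an investigator decision.
- That the primary ORR analysis is compromised by the row. A patient withdrawn before the first scan can drop out of the response-evaluable set, but that follows from the set's definition; the row only adds to it.

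**Conclusion.** The conflict is real and worth correcting: the Table 8.b row is wrong as written for life-threatening Grade 4 AEs not covered by 8.10. Read literally, it informatively censors PFS and OS in patients with the worst toxicity.

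The effect is probably small. It would cost an affected patient about 3 to 8 twelve-weekly contacts. The bound on OS overstatement in a cohort of 25 is 1.6 to 3.2 points for one missed death and 3.2 to 6.4 for two. These figures rest on assumed remaining time, assumed survival in the other patients, censoring before any other death, and a death that falls outside SAE reporting. If sites read the row as treatment withdrawal, the effect is zero.

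**What to change.** Reword the Table 8.b row to say: permanently discontinue modakafusp alfa; complete the EOT visit and continue safety, PFS and OS follow-up per Sections 6.3.1, 9.7 and 10.3; pembrolizumab is governed by Sections 8.6.4 and 8.6.4.2.

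The sponsor should confirm one point first. Section 8.6.4 lets a patient who stops modakafusp alfa continue pembrolizumab alone. Section 8.6.4.2 stops pembrolizumab for any life-threatening reaction other than an endocrinopathy controlled with hormone replacement. It is unclear whether that applies to an event attributed only to modakafusp alfa. If the row was meant to stop both drugs, it should say so.

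The cost is one table row and that decision. The visits already exist in the protocol, and sample size and analyses do not change. The change protects follow-up but does not guarantee a post-baseline scan, so it only partly addresses losses from the response-evaluable set.

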8.6.3.2 Pembrolizumab Dose Modification Guidelines

In this study, the dose of pembrolizumab cannot be modified. Depending on the toxicity observed, the infusion of pembrolizumab can be interrupted (in case of IRR, for example), delayed, or discontinued. If hypersensitivity or infusion-related events develop, the infusion should be temporarily slowed or interrupted, but dose modifications are not allowed. The patient should be treated according to the appropriate standard of care. Patients who discontinue pembrolizumab for reasons described in the pembrolizumab label other than irAEs may continue modakafusp alfa treatment.

General instructions:

1. It is recommended that the management of irAEs follow NCCN ([NCCN 2021](#)) or SITC ([Puzanov et al. 2017](#)) guidance. If pembrolizumab has been withheld, it can be resumed after the AE severity has decreased to Grade 1 or baseline level and corticosteroid has been tapered. Pembrolizumab should be permanently discontinued if the AE does not resolve within 12 weeks of last dose or corticosteroids cannot be reduced to ≤ 10 mg prednisone or equivalent per day within 12 weeks.
2. For severe and life-threatening irAEs, IV corticosteroid treatment should be initiated first followed by oral steroid therapy. Other immunosuppressive treatment should be initiated if irAEs cannot be controlled by corticosteroids.

Pembrolizumab dose modification guidelines for irAEs are detailed in [Table 8.c](#).

Table 8.c Pembrolizumab Dose Modification Guidelines for irAEs

Immune-Related AEs	Toxicity Grade or Conditions (CTCAE v5.0)	Action Taken with Pembrolizumab
Pneumonitis	Grade 2	Withhold.
	Grade 3 or 4, or recurrent Grade 2	Permanently discontinue.
Diarrhea/colitis	Grade 2 or 3	Withhold.
	Grade 4	Permanently discontinue.
AST/ALT elevation or increased bilirubin	Grade 2	Withhold.
	Grade 3 or 4	Permanently discontinue.
Type 1 diabetes mellitus or hyperglycemia	New onset type 1 diabetes mellitus or Grade 3 or 4 hyperglycemia associated with evidence of β -cell failure	Withhold.
Hypophysitis	Grade 2	Withhold.
	Grade 3 or 4	Withhold or permanently discontinue. ^a
Hyperthyroidism	Grade 2	Continue.
	Grade 3 or 4	Withhold or permanently discontinue.
Hypothyroidism	Grade 2 to 4	Continue.
Nephritis and renal dysfunction	Grade 2	Withhold.
	Grade 3 or 4	Permanently discontinue.
Myocarditis	Grade 1 or 2	Withhold.
	Grade 3 or 4	Permanently discontinue.

Table 8.c Pembrolizumab Dose Modification Guidelines for irAEs

Immune-Related AEs	Toxicity Grade or Conditions (CTCAE v5.0)	Action Taken with Pembrolizumab
All other immune-related AEs	Intolerable/persistent Grade 2	Withhold.
	Grade 3	Withhold or discontinue based on the type of event. Events that require discontinuation include, but are not limited to, Guillain-Barre Syndrome and encephalitis.
	Grade 4 or recurrent Grade 3	Permanently discontinue.

AE: adverse event; ALT: alanine aminotransferase; AST: aspartate aminotransferase; CTCAE: Common Terminology Criteria for Adverse Events; GI: gastrointestinal; irAE: immune-related adverse event; IV: intravenous.
^a Withholding or permanently discontinuing pembrolizumab is at the discretion of the investigator or treating physician.

For patients with Grade 3 or 4 immune-related endocrinopathy that does not require withholding of pembrolizumab, pembrolizumab may be resumed when the AE resolves to Grade ≤ 2 and is controlled with hormonal replacement therapy or metabolic control has been achieved (in case of type 1 diabetes mellitus).

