- Persistent Grade 2 or 3 adverse reactions (excluding endocrinopathies controlled with hormone replacement therapy) that do not recover to Grade ≤ 1 within 12 weeks after last dose of pembrolizumab.

- Any severe or Grade 3 treatment-related AE that recurs.

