10.2.1.2 Pembrolizumab

The following AEs are considered AESIs:

- Pneumonitis.
- Hepatitis.

- Colitis.
- Nephritis.
- Dermatologic reactions.
- Myocarditis.
- IRR.
- Endocrinopathies, including thyroid disorders, adrenal insufficiency, type 1 diabetes mellitus, and hypophysitis.

Serious AESIs will be reported to Takeda Global Pharmacovigilance in an expedited manner irrespective of the event's causal relationship. Further, patients will be advised to promptly report signs and symptoms that may indicate IRRs, including fever, chills, dizziness, nausea, vomiting, flushing, cough, headache, and rash during or soon after end of infusion.

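### The pembrolizumab restart sentence after Table 8.c excludes the withheld endocrine events it is meant for, and the general rule that then applies is inconsistent with the 12-week exclusion in Section 8.6.4.2

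*Protocol*

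**What the plan says.** Four pieces of the protocol bear on restarting or stopping pembrolizumab after an endocrine immune-related event.

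- **Table 8.c** (Section 8.6.3.2). The diabetes row, "New onset type 1 diabetes mellitus or Grade 3 or 4 hyperglycemia associated with evidence of" beta-cell failure, has the action withhold. Hypophysitis and hyperthyroidism at Grade 3 or 4 are withheld or permanently discontinued. Hypothyroidism at Grades 2 to 4 continues on treatment.
- **The sentence after Table 8.c.** It covers Grade 3 or 4 immune-related "endocrinopathy that does not require withholding of pembrolizumab, pembrolizumab may be resumed when the AE resolves to Grade" 2 or lower. The event must also be controlled with hormone replacement or, in type 1 diabetes, metabolic control must have been reached.
- **General instruction 1** (Section 8.6.3.2). If pembrolizumab was withheld, "it can be resumed after the AE severity has decreased to Grade 1 or baseline level and corticosteroid has been tapered". It adds: "Pembrolizumab should be permanently discontinued if the AE does not resolve within 12 weeks of last dose". Neither clause has an endocrine exception.
- **Section 8.6.4.2**, the list of permanent stops. One bullet reads "Any life-threatening adverse reaction (excluding endocrinopathies controlled with hormone replacement therapy"). Another reads "Persistent Grade 2 or 3 adverse reactions (excluding endocrinopathies controlled with hormone replacement therapy) that do not recover to Grade" 1 or lower within 12 weeks of the last dose.

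**The concern.** The restart sentence turns on a condition that defeats it: resuming presupposes that the drug was held, yet the sentence is confined to events for which it need not be held. It then gives type 1 diabetes as its example, which the table says to withhold. If the sentence is set aside, the only other restart threshold in the protocol is the stricter one in general instruction 1, and the 12-week stop there does not agree with the stop list in Section 8.6.4.2.

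What is at stake is a dosing decision. Two sites, each following a paragraph of the same protocol, could decide differently whether a patient whose endocrinopathy is stable on replacement goes back on pembrolizumab. The effect may extend to modakafusp alfa: Sections 8.6.3.2 and 8.6.4 let a patient continue it after stopping pembrolizumab for reasons other than immune-related events, which implies that a permanent stop for such an event does not carry that permission.

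**Working it through.** No sample size, power or error rate is involved and the plan gives no figure to reproduce. The check is a comparison of texts.

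**Step 1. Which withheld events does the restart sentence reach?** Table 8.c names four endocrine conditions. Each is tested against the sentence as written, then with permanent discontinuation in place of withholding.

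| Condition in Table 8.c | Action | Sentence as written | Sentence with the phrase replaced |
|---|---|---|---|
| New-onset type 1 diabetes, or Grade 3–4 hyperglycemia with beta-cell failure | Withhold | Does not apply: the event is withheld | Applies once metabolic control is reached |
| Hypophysitis, Grade 3–4 | Withhold or permanently discontinue | Does not apply | Applies if the drug was withheld and the event is controlled on replacement |
| Hyperthyroidism, Grade 3–4 | Withhold or permanently discontinue | Does not apply | Unclear: hormone replacement is not an obvious fit, and metabolic control is offered only for type 1 diabetes |
| Hypothyroidism, Grade 2–4 | Continue | Applies in terms, but nothing was stopped | No practical change |

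For hypophysitis and hyperthyroidism one could say that withholding is not strictly required, because discontinuation is the alternative. That does not rescue the sentence, since a permanently discontinued drug is not resumed either. As written, then, the sentence reaches no withheld event. The contradiction with the table is clear for type 1 diabetes and hypophysitis.

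**Step 2. Which rule is left?** For these events, general instruction 1: Grade 1 or baseline, with the corticosteroid tapered.

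**Step 3. Do the two 12-week rules agree?**

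| | General instruction 1 | Section 8.6.4.2 |
|---|---|---|
| Event clause | Stop if not resolved within 12 weeks of the last dose | Stop if a Grade 2 or 3 reaction has not reached Grade 1 or lower within 12 weeks of the last dose |
| Endocrine exception to that clause | None | Endocrinopathy controlled with hormone replacement |
| Corticosteroid clause | 10 mg prednisone or equivalent per day or less, within 12 weeks | Same limit |

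The rules differ only in the event clause, and clearly only for endocrinopathy controlled with hormone replacement. Hypophysitis is the plain case. Type 1 diabetes is arguable, because it depends on whether insulin counts as hormone replacement. Hyperthyroidism is not clearly within the exclusion.

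**Step 4. Worked case.** A patient has Grade 3 hypophysitis, pembrolizumab is withheld, and at 12 weeks the event is Grade 2 and stable on replacement.

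- Evident purpose of the sentence after Table 8.c: restart is allowed.
- General instruction 1, literally: restart is not allowed unless Grade 2 was the baseline, and if the event counts as unresolved the drug should be stopped for good.
- Section 8.6.4.2: the 12-week stop does not apply to this patient.

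**The case against.** The best reply is that this is a drafting slip whose purpose any clinician can see. Specific endocrine text would normally prevail over an instruction labelled general. That instruction says should and does not define resolution. An exclusion from a stop list is not an order to continue, so a site that always stops complies with both paragraphs. Section 8.6.4.2 also points to the product label, and Section 8.6.3.2 to outside irAE guidance.

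Part of this stands. The conflict is an inconsistency between rules, not a settled mandatory stop, and sites may resolve it sensibly. But the protocol does not say which paragraph prevails, the outside sources do not correct its wording, and always stopping would leave the Section 8.6.4.2 exclusion without effect.

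A reader might infer more than the documents support:

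- **That the corrected sentence would cover all three withheld conditions.** It would not clearly cover hyperthyroidism.
- **That a number of affected patients can be projected.** The documents give no rate for these events. Section 4.3.5 reports one Grade 3 adrenal insufficiency among 43 patients, but that is a different condition and a different combination, with nothing on whether pembrolizumab was withheld.
- **That ORR would be distorted.** No such effect is shown. Response assessment is calendar-based regardless of delays (Protocol Section 9.3.14), best response counts assessments after treatment discontinuation until subsequent therapy (SAP Section 7.9), and no formal efficacy test is planned (Protocol Section 13.4).
- **That the silence on Grade 2 hypophysitis and adrenal insufficiency is part of this error.** That is missing detail, separate from the sentence at issue.

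**Conclusion.** The point holds as an error in operative dosing text. Followed literally, the restart sentence applies to no withheld event and contradicts Table 8.c for type 1 diabetes and hypophysitis. The rule that takes over is inconsistent with Section 8.6.4.2 on the 12-week stop, clearly so for endocrinopathy controlled with hormone replacement.

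The likely intent is to let controlled endocrinopathy resume. This is an inference, but the protocol supports it elsewhere: exclusion criteria 2 and 13 (Section 7.2) accept endocrine deficiency on stable replacement, and the DLT definition (Section 8.2) excepts an asymptomatic Grade 3 endocrine disorder.

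The size is small. That few patients will be affected is a judgement, since the documents give no rate. Sample size, error rates and planned analyses do not change. The literal fallback is the more conservative rule, so the cost of the error is inconsistent re-dosing rather than a demonstrated safety harm.

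**What to change.** 1. In the sentence after Table 8.c, replace withholding by permanent discontinuation, with the sponsor confirming that this is what was meant.
2. In general instruction 1, add an exception for endocrinopathies controlled with hormone replacement, or with metabolic control in type 1 diabetes. It should apply to both the Grade 1 or baseline restart threshold and the 12-week event-resolution clause. The corticosteroid clause stays as it is.
3. Cross-refer that exception to the exclusions in Section 8.6.4.2. In doing so the sponsor should confirm that those exclusions are meant to reach type 1 diabetes under metabolic control, so that the two places agree.

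The cost is protocol wording only: one phrase, one exception and one cross-reference, which can go into the next amendment. The SAP needs no change.
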